3.5.4. Stopping rule for dose escalation

The safety review committee will decide to stop the dose escalation as planned per protocol in case of occurrence of:

- 2 subjects experiencing severe non serious AEs of the same organ class and nature related to the study drug,
- 4 subjects (for SAD) and 8 subjects (for MAD) experiencing study drug related moderate non serious AEs (that are considered directly related to the drug effect unless they resolved despite the continuation of the treatment),
- 2 subjects of the group experience a significant increase (i.e. $> 3 N$) ALAT,
- 2 subjects of the group experience simultaneous increases of total bilirubin ($> 2 N$), ALAT ($> 2 N$) and alkaline phosphatases ($> 1.5 N$),

- 2 subjects has a sustained QTc value > 500 ms (confirmed by a second ECG under strict resting position),
- One subject presents a C_{max} or $AUC_{(0-24h)}$ values respectively above 150 $\mu\text{g}/\text{mL}$ and 1000 $\mu\text{g}/\text{mL} \cdot \text{h}$,
- The mean C_{max} and $AUC_{(0-24h)}$ leads to believe taking into account the dose increase that C_{max} or $AUC_{(0-24h)}$ values of 125 $\mu\text{g}/\text{mL}$ and 600 $\mu\text{g}/\text{mL} \cdot \text{h}$ will be overpass with the following planned higher dose,
- In MAD part the mean at the steady state C_{max} and $AUC_{(t)}$ leads to believe taking into account the dose increase that C_{max} or $AUC_{(0-24h)}$ values of 125 $\mu\text{g}/\text{mL}$ and 800 $\mu\text{g}/\text{mL} \cdot \text{h}$ will be overpass with the following planned higher dose,

In one of the cases listed above, the dose group in progress will be stopped and the blind could be broken. Regarding laboratory and QTc abnormalities described above, if unblinding confirms that at least two subjects presenting these abnormalities were receiving the active drug the dose escalation will be stopped.

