3.3.3.2. Dose Escalation

The dose escalation is designed to progress from the first to the highest dose up to the occurrence of relevant events supporting Maximal Tolerated Dose (MTD) determination.

At the end of each dose level, an interim safety report will be issued by the Investigator. A dose escalation teleconference meeting will be held between the Investigator and the Sponsor representatives, and the decision on how to proceed (e.g. next higher dose) will be taken on the basis of a blind safety and pharmacokinetic data review.

The following safety parameters will be reviewed for both part, for all the subjects:

- Any adverse events reported;
- All laboratory parameters outside of ranges;

- Concomitant therapy;
- Physical examination abnormalities;
- Vital signs abnormalities;
- ECG abnormalities.

For dose escalation, Pharmacokinetic data on plasma (quantitative determination of DF2755A bound and unbound; qualitative and preliminary quantitative determination of known metabolites), urine and faeces recovery (qualitative and quantitative determination of parent compound and qualitative and preliminary quantitative investigation of known metabolites) will be considered by using, for each new dose level, the pharmacokinetic results of the previous dose level in order to re-estimate the safety margin based on the animal-human exposure ratio. This re-estimation must be taken into account when deciding whether to proceed to the next dose level.

The exposure does not exceed the AUC of 1000 $\mu\text{g}\cdot\text{h}/\text{mL}$.

Identification of non-acceptable risks or significant proportion of AEs with common pathological pattern can justify the modification of the dose escalation design.

After mutual agreement between the Sponsor and the Investigator and if it is considered useful for the selection of the next dose level, the treatment of a specific subject and/or a cohort may be unblinded before the next dose level of DF 2755A is administered.

At the end of the teleconference meeting, the following decisions can be taken:

- Dose escalation will continue as scheduled;
- An intermediate dose between the current dose and the following dose will be administered to the next cohort;
- A lower intermediate dose, between the current dose and the dose administered in the previous cohort will be administered to the next cohort;
- The current dose will be repeated in the next cohort;
- The study will be stopped.

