According to the conclusion of this meeting, the formal agreement/disagreement to move to a next cohort will be signed by both the Sponsor and the Investigator.

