3.5. Stopping rules

3.5.1. Stopping rule applicable at any time

In case of occurrence of a SAE at least possibly related to the study drug administration, the safety review committee will decide to put the study on hold, and will ask for unblinding for the subject. If the subject was treated by placebo, the study will be continued as planned per protocol. If the subject was receiving DF2755A, the study will be immediately interrupted and depending on the nature and SAE resolution it should be potentially re-started after submission and approval by both EC and CA of a substantial amendment.

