3.5.3. Stopping rules within a group

During the treatment period, the safety and tolerability will be evaluated on an ongoing basis, the following criteria will apply to stop the cohort :

- 2 subjects experiencing severe non serious AEs considered as at least possibly related to the study drug,
- 2 subjects experiencing a significant increase (i.e. $> 5N$) of ALAT (N being the upper limit of the normal value),

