8.3.2. Analysis of adverse events

The Investigator will evaluate the seriousness of any reported adverse event.

The Investigator will also evaluate each event with regard to its severity. The severity of the AEs will be determined in the following manner:

Mild	Grade 1 - Does not interfere with subject's usual function (awareness of symptoms or signs, but easily tolerated [acceptable]).
Moderate	Grade 2 - Interferes to some extent with subject's usual function (enough discomfort to interfere with usual activity [disturbing]).
Severe	Grade 3 - Interferes significantly with subject's usual function (incapacity to work or to do usual activities [unacceptable])

The Investigator will also evaluate the causality of the study treatment/product and any other treatments for each AE, and will transmit the result of this evaluation to the Sponsor. The possible relationship between the AE and the study product/treatment will be quoted as following:

None (Intercurrent Event)	An event that is not and cannot be related to the investigational product, e.g. patient is a passenger in a road traffic accident or surgical intervention performed during the study, but planned before patient enrolment into the study
Unlikely (remote)	Relationship is not likely e.g. a clinical event including laboratory test abnormality with temporal relationship to drug administration which makes a causal relationship improbable and in which other drugs, chemicals or underlying disease provide plausible explanations
Possible	Relationship may exist, but could have been produced by the patient's condition or treatment or other cause
Probable	Relationship is likely, the AE abates upon discontinuation of investigational product and cannot be due to the patient's condition
Highly Probable	Strong relationship, the event abates upon discontinuation of investigational product and, if applicable, re-appears upon repeat exposure
Not Assessable	Not possible to assess, because of insufficient evidence, conflicting data or poor documentation.

Also the Sponsor will evaluate serious adverse events which are reported by the Investigator, assessing causality with the study drug and any other treatments for each SAE and expectedness.

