12.3. Protocol amendments

Neither the Investigator nor the Sponsor can modify the protocol without agreement from the other party. Any protocol modifications must be the topic/matter of an amendment which will be dated and signed by the two parties and must be included as an addendum to the protocol.

Depending on the importance of the changes to the study conditions, the amendment may be sent to the Ethics Committee and/or Health Competent Authorities either for approval or for information.

A substantial protocol amendment must be submitted to the ANSM, in order to notify the results of SAD part of the study.

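### The moderate-AE stop in Protocol 3.5.4 leaves out worse events, so 3 moderate plus 1 severe (SAD) or 7 plus 1 (MAD) meets no AE-count trigger

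*Protocol*

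**What the plan says.** Four parts of the protocol bear on this.

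- **Section 3.5.4 (stopping escalation).** One AE criterion is "2 subjects experiencing severe non serious AEs of the same organ class and nature related to the study drug". The next is "4 subjects (for SAD) and 8 subjects (for MAD) experiencing study drug related moderate non serious AEs", with a qualifier about direct relation to the drug effect and about events that resolve while treatment continues.
- **Section 3.5.3 (stopping the cohort).** The AE criterion is "2 subjects experiencing severe non serious AEs considered as at least possibly related to the study drug". A shared organ class is not required.
- **Section 3.5.1 (any time).** This applies "In case of occurrence of a SAE at least possibly related to the study drug administration", so a severe but non-serious event is outside it. Section 3.5.2 stops an individual subject only.
- **Section 8.3.2 (severity).** Moderate is Grade 2. Severe is a separate category: "Grade 3 - Interferes significantly with subject's usual function".

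Nothing in the protocol or SAP says that a severe event counts towards the moderate total. Outside the stopping rules, section 3.3.3.2 says that the decision on how to proceed "will be taken on the basis of a blind safety and pharmacokinetic data review".

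**The concern.** A stopping rule for healthy volunteers should never become easier to pass because an event is worse. Section 3.5.4 names a severity category where it needs a severity floor. Replacing a moderate event by a severe one takes a subject out of the moderate count, and one severe subject is too few for either severe rule. The protocol does write a floor where it intends one, as in the causality wording of 3.5.1 and 3.5.3, so a floor cannot safely be read into the word moderate.

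Escalation would not then be automatic. It would depend on the judgement of the sponsor and investigator at the dose-escalation meeting, where a pre-stated stop should apply.

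**Working it through.** The protocol gives no derivation or operating characteristics for the thresholds, so there is no figure of its own to reproduce. The check lists the outcomes and then gives their probabilities.

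**Inputs from the protocol.** SAD: 8 per cohort, 6 active, threshold T = 4. MAD: 12 per cohort, 9 active, T = 8 (sections 1.6 and 3.5.4).

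**Definitions.** Let m be the number of subjects whose worst related non-serious AE is moderate, and s the number whose worst is severe.

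- AE count met as written: m ≥ T or s ≥ 2 (the second part is 3.5.3).
- AE count met with a floor: m + s ≥ T or s ≥ 2.
- Escaping outcomes: m + s ≥ T, m < T and s < 2. These force s = 1 and m = T − 1.

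| Part | m, s | As written | With a floor |
|---|---|---|---|
| SAD | 4, 0 | 3.5.4 met | met |
| SAD | 3, 1 | none met | met |
| SAD | 2, 2 | 3.5.3 met | met |
| MAD | 8, 0 | 3.5.4 met | met |
| MAD | 7, 1 | none met | met |
| MAD | 6, 2 | 3.5.3 met | met |

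One pattern per part escapes: (3, 1) and (7, 1). The same holds if placebo subjects enter the blinded count (8 or 12 subjects).

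**How often.** AE rates are not in the documents, so they are assumed: per-subject probabilities p (worst event moderate) and q (worst event severe), with independent subjects and active subjects only.

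- SAD: P(3, 1) = 6!/(3! 1! 2!) × p³ × q × (1 − p − q)² = 60 p³ q (1 − p − q)². At 0.4/0.1: 60 × 0.064 × 0.1 × 0.25 = 0.096.
- MAD: P(7, 1) = 9!/(7! 1! 1!) × p⁷ × q × (1 − p − q) = 72 p⁷ q (1 − p − q). At 0.6/0.1: 72 × 0.02799 × 0.1 × 0.3 = 0.0605.

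SAD results:

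| p/q | P(3, 1) | P(at least 4 of 6 affected) | Ratio |
|---|---|---|---|
| 0.1/0.02 | 0.00093 | 0.00254 | 37% |
| 0.2/0.05 | 0.0135 | 0.0376 | 36% |
| 0.3/0.05 | 0.0342 | 0.1174 | 29% |
| 0.4/0.1 | 0.0960 | 0.3438 | 28% |
| 0.5/0.1 | 0.1200 | 0.5443 | 22% |

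MAD, P(7, 1): 0.0005 at 0.3/0.05, 0.0059 at 0.4/0.1 and 0.0605 at 0.6/0.1.

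**Effect of a floor on the chance that an AE count (3.5.3 or 3.5.4) is met.**

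| Part, p/q | As written | With a floor |
|---|---|---|
| SAD, 0.2/0.05 | 5.0% | 6.3% |
| SAD, 0.4/0.1 | 29.0% | 38.6% |
| SAD, 0.5/0.1 | 44.9% | 56.9% |
| MAD, 0.4/0.1 | 22.9% | 23.5% |
| MAD, 0.6/0.1 | 29.6% | 35.6% |

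**The case against.** The best defence is that the pattern would be caught anyway. Section 3.3.3.2 has every AE reviewed, allows unblinding, offers repeat, lower-dose and stop options, and requires the agreement or disagreement "to move to a next cohort will be signed by both the Sponsor and the Investigator". Escalation is meant to run only until events support an MTD, which section 3.2 defines as the highest dose free of clinical signs or symptoms. Three moderate and one severe related event on active drug would be past it. The investigator may also suspend the study alone (4.4.2.2). And 3.5.4 is itself worded as a committee decision, so a committee could well treat a severe event as at least moderate. All of this makes escalation past the pattern less likely. None of it is a stated count, and 3.5.4 exists to fix the decision in advance.

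Two points on the numbers stand in part.

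- The figures depend on assumed rates and put each subject in one category. A subject with a severe event and a separate qualifying moderate event already counts towards 4 or 8, so at given rates the escape probabilities are upper bounds in that respect.
- The baseline credits 3.5.3, which stops the cohort; 3.5.4 by itself needs severe events of the same class and nature. If severe events never share a class, the chance of meeting 3.5.4's AE counts in SAD at 0.4/0.1 rises from 17.9% to 34.4%. That is 16.5 points, against 9.6 when 3.5.3 is credited. On that reading both the gap and the cost of closing it are larger.

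**Conclusion.** The concern holds. As written, the AE-count triggers are not monotone in severity: 4 + 0 (SAD) and 8 + 0 (MAD) meet a stated stop, while 3 + 1 and 7 + 1 meet none. This is an error in a stated safety rule and should be corrected.

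It assumes that the affected subjects are different people, the severe subject has no separate qualifying moderate AE, all events are non-serious, the moderate events satisfy the criterion's own qualifier, and no laboratory, QTc or PK trigger is met.

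The size is modest. Over the SAD rates tabulated, the pattern occurs in 0.1% to 12.0% of cohorts, and in 22% to 37% of those with at least four active subjects affected. In MAD it stays at 0.6% or less up to 0.4/0.1. The logical result does not depend on the assumed rates; the frequencies do.

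**What to change.** In the second AE criterion of 3.5.4, replace the severity term with *moderate or severe (Grade 2 or higher)*, and state that each subject counts once, by the worst related non-serious AE. Keep the thresholds of 4 and 8 and the existing qualifier.

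The edit is one phrase plus that counting sentence. The price is more stops: 9.6 points in SAD at 0.4/0.1 and 12.0 at 0.5/0.1, but under 1 point in MAD at 0.4/0.1 or lower. With 3.5.3 credited, every added stop is a 3 + 1 or 7 + 1 cohort, which is worse than one that already stops.

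To protect Part A the change must be in force before SAD dosing. SAP section 2.1 describes allocation in the past tense, so that may no longer be possible. Part B can still be covered, because section 12.3 already requires a pre-MAD filing: "A substantial protocol amendment must be submitted to the ANSM, in order to notify the results of SAD part of the study".

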3.5.2. Stopping rule for a subject

During the treatment period, the safety and tolerability will be evaluated on an ongoing basis, the following criteria will apply to stop a subject:

- The subject experiences an AE that prevents him from continuing in the study,
- Significant increase (i.e. $> 3N$) of ALT (N being the upper limit of the normal value),
- Abnormal laboratory results with simultaneous increases of total bilirubin ($> 2 N$), ALT ($> 2 N$) and alkaline phosphatases ($> 1.5 N$),
- The subject develops a serum creatinine ≥ 2 times the ULN,
- Sustained QTcF value of > 500 msec confirmed by at least one repeat ECG,
- The subject withdraws consent,
- At the request of the Sponsor or at the Investigator's request (for example if the Investigator considers that the subject's health is compromised by remaining in the study or the subject is not sufficiently cooperative).

See also Section 3.6 "Removal of Subjects from Therapy or Assessment".

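### Serum creatinine at or above 2 × ULN stops a subject but, unlike the other three numeric subject limits, has no two-subject stopping trigger for the group

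*Protocol*

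**What the plan says.** Protocol section 3.5.2 lists, among the reasons to stop a subject, four with numeric limits: ALT above 3N; simultaneous rises of total bilirubin (above 2N), ALT (above 2N) and alkaline phosphatase (above 1.5N); creatinine ("The subject develops a serum creatinine" of at least twice the ULN); and a sustained, confirmed QTcF above 500 ms.

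Section 3.5.4 gives two-subject rules for ALAT above 3N ("2 subjects of the group experience a significant increase"), for the same liver combination and for sustained QTc above 500 ms. The consequence is stated there: "In one of the cases listed above, the dose group in progress will be stopped and the blind could be broken". For the laboratory and QTc items it lists, "if unblinding confirms that at least two subjects presenting these abnormalities were receiving the active drug the dose escalation will be stopped".

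The other count rules concern adverse events. Section 3.5.3 stops a cohort for "2 subjects experiencing severe non serious AEs considered as at least possibly related to the study drug", or for ALAT above 5N in two subjects. Section 3.5.4 also counts severe related events of the same organ class and nature in two subjects, and "4 subjects (for SAD) and 8 subjects (for MAD) experiencing study drug related moderate non serious AEs". Section 3.5.1 provides a study hold: "In case of occurrence of a SAE at least possibly related to the study drug administration", the committee suspends the study and the subject is unblinded.

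**The concern.** A creatinine of at least 2 × ULN is serious enough, by the protocol's own limit, to take a volunteer off drug. Two such volunteers in one cohort nevertheless trigger no group rule, whereas two with ALAT above 3N do. No reason for the difference is given. What happens to the rest of the cohort, and to the next dose, then depends on someone deciding to act.

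This matters mainly in Part B, where 14 days of twice-daily dosing leave time for other subjects to go on receiving a dose that has already produced two renal stops.

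**Working it through.** **1. Matching the rules.**

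| Numeric limit for a subject (3.5.2) | Group rule in 3.5.3 | Two-subject rule in 3.5.4 |
|---|---|---|
| ALT > 3N | only at > 5N | yes, > 3N |
| Bilirubin > 2N, ALT > 2N, ALP > 1.5N together | no | yes |
| Creatinine ≥ 2 × ULN | no | **no** |
| QTcF > 500 ms, sustained | no | yes (QTc) |

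Four limits, three matched in 3.5.4, one unmatched: 4 − 3 = 1. The closing sentence of 3.5.4 covers only the abnormalities it has listed, so it does not bring creatinine in. With the creatinine upper limits in the SAP laboratory ranges, the threshold is 2 × 104 = 208 µmol/L for men and 2 × 84 = 168 µmol/L for women.

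**2. Whether the adverse-event counts cover it.** Protocol 8.3.2 grades severity only by effect on usual function and has no laboratory scale. A symptom-free creatinine rise reads most naturally as mild, although the Investigator could grade it higher. Mild events count toward nothing in 3.5.3 or 3.5.4. On that reading no numeric group rule is met even if all 6 active subjects of a Part A cohort, or all 9 of a Part B cohort, reach the limit. If every rise were graded moderate and related, 4 subjects (Part A) or 8 (Part B) would be needed instead of 2.

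The documents give no event rate. As an illustration, let p be an assumed probability that an active subject reaches the limit. The chance of at least r cases among n active subjects is the binomial tail P(X ≥ r):

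| p | ≥ 2 of 6 | ≥ 4 of 6 | ≥ 2 of 9 | ≥ 8 of 9 |
|---|---|---|---|---|
| 0.10 | 0.114 | 0.001 | 0.225 | 0.000 |
| 0.20 | 0.345 | 0.017 | 0.564 | 0.000 |
| 0.30 | 0.580 | 0.071 | 0.804 | 0.0004 |
| 0.50 | 0.891 | 0.344 | 0.980 | 0.020 |

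**3. Dosing left in Part B.** Assumptions: the example stagger of 3.3.3.1 (2, 3, 3 and 4 subjects starting on days 1 to 4); one placebo among the first two (3.3.1); same-day laboratory results; both active cases found at the same visit; no judgement-based hold. A subject starting on calendar day s has visit Dk on day s + k − 1 and the last dosing day on s + 13. The second case is known on day c = (later start of the two) + k − 1. Only one of the first two subjects is active, so the later start is day 2, 3 or 4. Dosing days left for another subject = max(0, s + 13 − c).

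At D5, c runs from 2 + 4 = 6 to 4 + 4 = 8. Fewest days: s = 1, c = 8, 14 − 8 = 6. Most: s = 4, c = 6, 17 − 6 = 11. The other 12 − 2 = 10 subjects comprise 9 − 2 = 7 active and 3 placebo. Over the 7 active, the lowest total is 6 + 3×7 + 3×8 = 51 (c = 8, both cases and both later placebos starting on day 4). The highest is 3×10 + 4×11 = 74 (c = 6, cases starting on days 1 and 2, both later placebos starting on day 2).

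| Visit of the two cases | c (calendar day) | Days left per other subject | Total over 7 active |
|---|---|---|---|
| D5 | 6–8 | 6–11 | 51–74 |
| D7 | 8–10 | 4–9 | 37–60 |
| D10 | 11–13 | 1–6 | 16–39 |
| D14 | 15–17 | 0–2 | 0–11 |

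All are upper bounds, because each remaining subject is retested at the visits still ahead (D5, D7, D10, D14) and stopped individually at the same limit.

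**4. Part A.** With 2, 3 and 3 subjects starting on days 1 to 3 and a laboratory test on D2, a second active case is known on day 3 or 4 at the earliest. All 8 subjects are dosed by day 3, so the rule would in practice affect escalation only.

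**The case against.** Nothing in the protocol requires group rules to mirror subject rules, and it does not do so throughout: 3.5.3 uses ALAT above 5N and omits both the liver combination and QTc. If 3.5.4 always stopped the dose group at 3N, the 5N rule would be redundant. Read as its title suggests, 3.5.4 may concern escalation alone, and the Part B dosing-day figures would then fall away.

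Escalation is already reviewed. Section 3.3.3.2 puts every out-of-range laboratory value before the meeting, allows unblinding, and lets a common pathological pattern among adverse events justify changing the scheme. Within a cohort, a creatinine stop in Part B is recordable as an adverse event because it ends dosing (8.3.1). One case judged an important medical event, at least possibly related and on active drug, interrupts the whole study under 3.5.1, which is stricter than a two-subject rule. The new-event provision (8.3) and suspension by the Sponsor or Investigator (4.4.2) can also act at once.

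The biology is thin. Both 7-day range-finding studies showed tubular degeneration, but raised creatinine appeared only in dogs, at 900 mg/kg/day, 900/40 = 22.5 times the dog NOAEL. In the 28-day studies dogs had no clinical-pathology effect up to 200 mg/kg/day, creatinine fell in female rats, and the kidney changes were judged adaptive.

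Much of this stands: the impact is uncertain and a strong renal signal is absent. It does not remove the gap. Section 3.5.4 says outright that the dose group in progress stops, and an overlapping 5N rule elsewhere does not cancel that sentence. None of the alternative routes sets a creatinine limit; each rests on judgement. Signal strength does not explain the selection either: the protocol calls liver and kidney changes adaptive in the same sentence, and QTc has a group rule despite no I_Kr inhibition up to 1 mM.

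**Conclusion.** The omission is certain: one of four numeric subject limits has no group counterpart. Its consequence is modest and less certain. Escalation loses a fixed trigger in both parts. In Part B, taking 3.5.4 as written, two active cases at D5 could be followed by at most 6 to 11 further dosing days for each other subject, or 51 to 74 in total over the 7 remaining active subjects, and less at later visits. Those figures depend on the example stagger, same-day results, both cases at one visit and no discretionary hold. The documents do not say how likely two cases are. Individual protection continues and no data are lost, since all laboratory values are listed and flagged (protocol 10.1.2.3, SAP 4.5). The argument is consistency with the protocol's own limit; this is a change to consider.

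**What to change.** Add one line to protocol 3.5.4: two subjects of the group with serum creatinine ≥ 2 × ULN. Place it under the existing condition that unblinding must confirm at least two are on active drug before escalation stops. The adverse-event grading scale need not change.

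This alters a binding stopping limit and so needs an amendment. Part B cannot start without a substantial amendment anyway (1.4, 12.3), and the line can go in with it. The cost is an occasional earlier pause, sometimes for a placebo case until the code is opened.
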